8.3 Efficacy Analysis

Response assessments will be performed as described in Section 7.1.2.5.

8.3.1 Primary Efficacy Endpoint

The primary efficacy endpoint is the overall response rate (CR + PR for FL and MZL) and will be calculated for all treated patients. The corresponding 95% two-sided confidence interval will be derived.

8.3.2 Secondary Efficacy Endpoints

8.3.2.1 Duration of response

Duration of response will be measured from the time by which the measurement criteria are met for CR or PR, whichever is recorded first, until death or the first date by which recurrent or progressive disease is objectively documented. Subjects who are progression-free and alive at the time of clinical cut-off or have unknown status will be censored at the last tumor assessment.

Non-responders will be excluded from the analysis of DOR. Kaplan Meier methodology will be used to estimate event-free curves.

8.3.2.2 Progression-free survival

PFS will be measured for each disease cohort as time from the first study drug administration to the first occurrence of lymphoma progression or death from any cause.

Data for subjects without disease progression or death will be censored at the date of the last tumor assessment. Kaplan-Meier methodology will be used to estimate the event-free curves.

8.3.2.3 Time to next therapy

Time to additional anti-neoplastic treatment will be measured from the time of first study drug administration until the date of the first subsequent therapy given to treat the iBCL. Data for subjects that have not received additional anti-neoplastic therapy will be censored at the date of last known contact.

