2.0 TRIAL DESIGN

2.1 Trial Design

This is a single arm phase II pilot study evaluating the efficacy of single-agent pembrolizumab for untreated, indolent B-cell non-Hodgkin lymphoproliferative diseases (iBCL) including follicular lymphoma (FL) and marginal zone lymphoma (MZL). In the window phase, treatment will be administered for up to six 3-week cycles and a response assessment performed at the conclusion. Patients that tolerate the drug and meet criteria for an objective response after 6 cycles may continue to receive pembrolizumab for up to an additional 12 cycles in the continuation phase. Patients who show progressive disease or stable disease after 6 cycles may be restaged after 3 additional cycles to assess for pseudoprogression/delayed response. Patients who show disease progression after 3 additional cycles will be removed from treatment. Patients who do not show evidence of disease progression may continue to receive pembrolizumab for up to a total of 18 cycles. A futility analysis will be performed after the first 5 subjects in each of two histologic subgroups (follicular lymphoma, marginal zone lymphoma) are treated. We anticipate that subjects will be enrolled over approximately 18 months and will be followed for outcomes for up to 5 years using standard-of-care assessments.

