3.2 Secondary Objectives & Hypotheses

(1) Objective:

To assess the safety and toxicity profile of pembrolizumab in patients with untreated iBCL.

Hypothesis: Pembrolizumab will not cause a significant degree of toxicity.

(2) Objective:

To measure the efficacy of pembrolizumab used as monotherapy for patients with untreated iBCL by assessing clinical outcomes including complete response rate (CR), clinical benefit rate (CBR) defined as CR+partial response (PR)+ stable disease (SD) $\times \geq 6$ months, time to next therapy (TNT), progression-free survival (PFS), and the duration of response (DOR).

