7.1.5.3 End-of-treatment Visit

Thirty days (+/- 14 d) after the last dose of pembrolizumab, irrespective of cause of cessation, an end-of-treatment visit should be performed. However, if a subject requires additional anti-cancer therapy, the off-study visit may occur earlier.

The off-study visit will include laboratory studies, medical history, physical exam, remission status, concomitant medications, adverse events, and documentation of any ECI and subsequent management, as in Section 6.0. All AEs that occur prior to the end-of-treatment visit should be recorded. Subjects with an AE of Grade > 1 will be followed until the resolution of the AE to Grade 0-1 or until the beginning of a new anti-neoplastic therapy, whichever occurs first. SAEs that occur within 90 days of the end of treatment or before initiation of a new anti-cancer treatment should also be followed and recorded.

After the end-of-study visit, additional follow-up will be conducted as per routine standard of care for up to 5 years unless other criteria for withdrawal are met (see Section 5.6). Long-term follow-up may be performed at patients' local physician's offices. Long-term follow-up will assess survival and disease progression; for clarification, subjects may be contacted by the study team until death, subject withdrawal of consent, lost to follow-up, or study termination, whichever occurs first.

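### Time to next therapy censors patients who die without further treatment, so a Kaplan-Meier curve would overstate both the probability of next therapy and the proportion alive without it (minor)

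*Combined protocol and SAP*

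**What the plan says.** Section 8.3.2.3 measures TNT from the first dose "until the date of the first subsequent therapy given to treat the iBCL". Its censoring rule is: "Data for subjects that have not received additional anti-neoplastic therapy will be censored at the date of last known contact". Death is not mentioned, so a patient who dies without further treatment falls under that rule by implication. The section names no estimator.

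The two neighbouring endpoints handle death explicitly. PFS (Section 8.3.2.2) runs to "the first occurrence of lymphoma progression or death from any cause". DOR (Section 8.3.2.1) runs "until death or the first date by which recurrent or progressive disease is objectively documented". Both name Kaplan-Meier; for PFS the text is "Kaplan-Meier methodology will be used to estimate the event-free curves".

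Section 3.2 lists TNT with PFS and DOR among the secondary efficacy outcomes and attaches no hypothesis to it. Under Section 2.1 patients "will be followed for outcomes for up to 5 years using standard-of-care assessments". Section 7.1.5.3 states that "Long-term follow-up will assess survival and disease progression", and the flow chart in Section 6.1 lists both survival status and post-study anticancer therapy status in long-term follow-up.

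**The concern.** Censoring is meant for patients who could still have the event after they leave observation. A patient who has died cannot start another therapy. Kaplan-Meier nevertheless treats a censored death as someone who would go on to start therapy at the same rate as the survivors.

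The resulting curve answers neither question a reader would ask of TNT. It does not give the probability that a patient goes on to receive another lymphoma therapy, because it credits the dead with future treatment. Nor does it give the proportion alive and off further treatment, because deaths do not bring it down. What is at stake is the interpretation of one secondary endpoint, which would probably be shown beside PFS and DOR curves that do count death.

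**Working it through.** **The plan's own figures.** The documents state no figure for TNT, so there is none to reproduce. The one power statement concerns ORR (Section 8.2: 33 patients, 25% against 50%, continue on 5 or more of 16, success on 13 or more of 33). Exact two-stage binomial calculation gives power 0.902 and one-sided alpha 0.0449, in line with the stated 90% and .05. TNT plays no part in it.

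**Direction, without any rate assumption.** At each event time let n be the number at risk, a the number starting next therapy and b the number dying without it.

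- Kaplan-Meier with deaths censored: K = product of (1 − a/n).
- Proportion alive without new therapy: A = product of (1 − (a + b)/n). Each factor is no larger than its counterpart in K, so A ≤ K.
- Cumulative incidence of next therapy: C = sum of A(just before) × a/n. Since A ≤ K, this is at most the sum of K(just before) × a/n, which equals 1 − K. So C ≤ 1 − K.

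Hence A ≤ K ≤ 1 − C in any data set. The planned curve lies above the proportion alive without new therapy and below the proportion who have not received next therapy once death is treated as competing.

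**Size, under stated assumptions.** Neither rate is in the documents. I assume constant yearly hazards: l = 0.12 for next therapy and d = 0.03 (range 0.01 to 0.05) for death without it. The horizon is t = 5 years, the maximum follow-up in Section 2.1.

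- Treated, deaths censored: 1 − exp(−l·t) = 1 − exp(−0.60) = 0.451.
- Treated, cumulative incidence: l/(l + d) × [1 − exp(−(l + d)·t)] = 0.80 × [1 − exp(−0.75)] = 0.422.
- Treated or dead: 1 − exp(−(l + d)·t) = 1 − exp(−0.75) = 0.528.
- Death without therapy: 0.528 − 0.422 = 0.106.

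| Yearly hazard of death without therapy | Treated, deaths censored | Treated, cumulative incidence | Treated or dead |
|---|---|---|---|
| 0.01 | 45.1% | 44.1% | 47.8% |
| 0.03 | 45.1% | 42.2% | 52.8% |
| 0.05 | 45.1% | 40.4% | 57.3% |

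Censoring deaths therefore overstates the probability of next therapy by 45.1 − 42.2 = 2.9 points (1.0 to 4.7). It puts the event-free curve at 54.9%, against 47.2% alive without new therapy, a gap of about 7.6 points (2.7 to 12.1).

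**A second set of assumptions.** Fix the 5-year Kaplan-Meier risk of next therapy at 50% and the 5-year net risk of death without it at 2%, 5%, 10% or 20%.

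- Kaplan-Meier, free of next therapy: 50.0% throughout.
- One minus cumulative incidence: 50.4%, 51.1%, 52.3%, 54.6%.
- Alive without new therapy: 49.0%, 47.5%, 45.0%, 40.0%.

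**Scale against precision.** With 33 patients and no earlier censoring, the binomial standard error of a 45% estimate is √(0.45 × 0.55/33) = 0.087, a 95% half-width of about 17 points. Under the main assumption about 33 × 0.106 = 3.5 patients would die without next therapy within 5 years (1.2 to 5.6 over the range).

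**The case against.** The strongest reply is that this is a small matter on an untested secondary endpoint in a single-arm pilot. Early deaths are not hidden: PFS counts them, DOR counts them among responders, and survival is followed. TNT measures something other than PFS, so a different event definition is not in itself a contradiction. Section 8.3.2.3 does not say Kaplan-Meier will be used, and the assumed rates have no support in the documents. If few patients die untreated, the estimates barely differ. One could add that censoring at death is legitimate when only the rate of next therapy among survivors is wanted.

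Most of this stands, and it limits the point to a minor one. It does not remove it. The censoring rule is stated, it covers the dead, and no planned analysis turns the rate among survivors into a probability of treatment. Kaplan-Meier is an inference from Sections 8.3.2.1 and 8.3.2.2; naming the estimator is part of the repair.

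A reader might infer that censoring deaths simply flatters the drug by making treatment-free time look longer. That holds only against time alive without new therapy (54.9% against 47.2%). Against the cumulative incidence of next therapy the error runs the other way: 45% appear treated rather than 42%, which is unfavourable to the drug. A reader might also turn the hazards into medians. The Kaplan-Meier median would be ln 2/0.12 = 5.8 years, beyond the 5 years of follow-up, so it would not be reached and should not be used as evidence.

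**Conclusion.** The point holds as a minor one. The rule in Section 8.3.2.3 censors patients who die without next therapy although death rules that therapy out. If the analysis is Kaplan-Meier, the curve overstates the probability of next therapy and also overstates the proportion alive without it. The direction needs no rate assumption.

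The size does. With yearly hazards of 12% for next therapy and 3% (1% to 5%) for death without it, the 5-year figures are 45% treated with deaths censored, 42% (44% to 40%) by cumulative incidence, and 53% (48% to 57%) treated or dead. These rest on constant hazards that the documents do not supply, and the differences lie within the sampling error of 33 patients.

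The documents do not support a reading that the trial's main conclusion is at risk: ORR, sample size, power and the stopping rules do not depend on TNT.

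**What to change.** In Section 8.3.2.3:

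- Define death before the next iBCL therapy as a competing event.
- Name the Aalen-Johansen estimator, and report the cumulative incidence of next therapy together with that of death without it. One minus their sum is the proportion alive without new therapy, so both quantities are available.
- Censor at last known contact only patients who are alive and have had no new therapy.

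The cost is a change of SAP wording and a little more analysis in standard software. The flow chart already lists survival and later anticancer therapy in long-term follow-up, so no new data item is needed. The downside for the sponsor is that the proportion shown as alive off therapy will be somewhat lower than a Kaplan-Meier curve with deaths censored would suggest.

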8.3.2.4 Safety Analysis

Adverse events and serious adverse events will be reviewed internally on an ongoing basis to identify safety concerns. Safety summaries will include tabulations in the form of tables. The frequency of treatment-emergent AE's will be summarized. Additional AE summaries will include AE frequency by AE severity and relationship to the study drug.

AE's requiring discontinuation of the study drug will be summarized separately, both overall and by AE severity and by relationship to the study drug. Clinically significant abnormal laboratory values will be summarized over study visits.

8.3.2.5 Biomarkers

Biomarker data will be collected on all subjects enrolled on study and examined for correlation of response to pembrolizumab in aggregate and within disease subtypes cohorts. Descriptive statistics will be used for hypothesis-generating endpoints.

9.0 LABELING, PACKAGING, STORAGE AND RETURN OF CLINICAL SUPPLIES

9.1 Investigational Product

The investigator shall take responsibility for and shall take all steps to maintain appropriate records and ensure appropriate supply, storage, handling, distribution and usage of investigational product in accordance with the protocol and any applicable laws and regulations.

Clinical Supplies will be provided by Merck as summarized in Table 7.

Table 7 Product Descriptions

Product Name & Potency	Dosage Form
Pembrolizumab 50 mg	Lyophilized Powder for Injection

Product Name & Potency	Dosage Form
Pembrolizumab 100 mg/ 4mL	Solution for Injection

9.2 Packaging and Labeling Information

Clinical supplies will be affixed with a clinical label in accordance with regulatory requirements.

9.3 Clinical Supplies Disclosure

This trial is open-label; therefore, the subject, the trial site personnel, the Sponsor-Investigator and/or designee are not blinded to treatment. Drug identity (name, strength) is included in the label text; random code/disclosure envelopes or lists are not provided.

9.4 Storage and Handling Requirements

Clinical supplies must be stored in a secure, limited-access location under the storage conditions specified on the label.

Receipt and dispensing of trial medication must be recorded by an authorized person at the trial site.

Clinical supplies may not be used for any purpose other than that stated in the protocol.

9.5 Returns and Reconciliation

The investigator is responsible for keeping accurate records of the clinical supplies received from Merck or designee, the amount dispensed to and returned by the subjects and the amount remaining at the conclusion of the trial.

Upon completion or termination of the study, all unused and/or partially used investigational product will be destroyed at the site per institutional policy. It is the Investigator's responsibility to arrange for disposal of all empty containers, provided that procedures for proper disposal have been established according to applicable federal, state, local and institutional guidelines and procedures, and provided that appropriate records of disposal are kept.

10.0 ADMINISTRATIVE AND REGULATORY DETAILS

10.1 Data and Safety Monitoring Plan

Ongoing trial oversight is carried out by the Principal Investigator and study staff. These individuals will communicate on a regular basis to review recently acquired data and adverse events. The data recorded within the research charts and protocol database is compared with the actual data that is available from the medical record and/or clinical histories. Data detailed

in the research case report forms includes the nature and severity of all toxicities, which are also reported as described above.

Institutional support of trial monitoring will be in accordance with the Fred Hutch/University of Washington Cancer Consortium Institutional Data and Safety Monitoring Plan. Under the provisions of this plan, Fred Hutch Clinical Research Support coordinates data and compliance monitoring conducted by consultants, contract research organizations, or Fred Hutch employees unaffiliated with the conduct of the study. Independent monitoring visits occur at specified intervals determined by the assessed risk level of the study and the findings of previous visits per the institutional DSMP.

In addition, protocols are reviewed at least annually and as needed by the Consortium Data and Safety Monitoring Committee (DSMC), Fred Hutch Scientific Review Committee (SRC) and the Fred Hutch/University of Washington Cancer Consortium Institutional Review Board (IRB). The review committees evaluate accrual, adverse events, stopping rules, and adherence to the applicable data and safety monitoring plan for studies actively enrolling or treating patients. The IRB reviews the study progress and safety information to assess continued acceptability of the risk-benefit ratio for human subjects. Approval of committees as applicable is necessary to continue the study.

The trial will comply with the standard guidelines set forth by these regulatory committees and other institutional, state, and federal guidelines.

10.2 Records

Research staff under the supervision of the investigators will maintain case report forms and secured databases on the relevant clinical and laboratory data. Records maintained in investigators' offices will be secured with access limited to study personnel. Authorization for access to medical records will be obtained from all patients in accordance with provisions of the Health Insurance Portability and Accountability Act (HIPAA).

11.0 APPENDICES

11.1 ECOG Performance Status

Grade	Description
0	Normal activity. Fully active, able to carry on all pre-disease performance without restriction.
1	Symptoms, but ambulatory. Restricted in physically strenuous activity, but ambulatory and able to carry out work of a light or sedentary nature (e.g., light housework, office work).
2	In bed <50% of the time. Ambulatory and capable of all self-care, but unable to carry out any work activities. Up and about more than 50% of waking hours.
3	In bed >50% of the time. Capable of only limited self-care, confined to bed or chair more than 50% of waking hours.
4	100% bedridden. Completely disabled. Cannot carry on any self-care. Totally confined to bed or chair.
5	Dead.

* As published in Am. J. Clin. Oncol.: *Oken, M.M., Creech, R.H., Tormey, D.C., Horton, J., Davis, T.E., McFadden, E.T., Carbone, P.P.: Toxicity And Response Criteria Of The Eastern Cooperative Oncology Group. Am J Clin Oncol 5:649-655, 1982.* The Eastern Cooperative Oncology Group, Robert Comis M.D., Group Chair.

11.2 Common Terminology Criteria for Adverse Events V4.0 (CTCAE)

The descriptions and grading scales found in the revised NCI Common Terminology Criteria for Adverse Events (CTCAE) version 4.0 will be utilized for adverse event reporting. (<http://ctep.cancer.gov/reporting/ctc.html>)

11.3 Response Evaluation

11.3.1 The Lugano Response Classification: For FL and MZL (18)

Response and Site	PET-CT-Based Response	CT-Based Response
Complete	Complete metabolic response Score 1, 2, or 3* with or without a residual mass on 5PS [†] It is recognized that in Waldeyer's ring or extranodal sites with high physiologic uptake or with activation within spleen or marrow (eg, with chemotherapy or myeloid colony-stimulating factors), uptake may be greater than normal mediastinum and/or liver. In this circumstance, complete metabolic response may be inferred if uptake at sites of initial involvement is no	Complete radiologic response (all of the following) Target nodes/nodal masses must regress to ≤ 1.5 cm in LD _i No extralymphatic sites of disease
Lymph nodes and extralymphatic sites		

Response and Site	PET-CT-Based Response	CT-Based Response
	greater than surrounding normal tissue even if the tissue has high physiologic uptake	
Nonmeasured lesion	Not applicable	Absent
Organ enlargement	Not applicable	Regress to normal
New lesions	None	None
Bone marrow	No evidence of FDG-avid disease in marrow	Normal by morphology; if indeterminate, IHC negative
Partial	Partial metabolic response	Partial remission (all of the following)
Lymph nodes and extralymphatic sites	Score 4 or 5 [†] with reduced uptake compared with baseline and residual mass(es) of any size	≥ 50% decrease in SPD of up to 6 target measurable nodes and extranodal sites
	At interim, these findings suggest responding disease	When a lesion is too small to measure on CT, assign 5 mm × 5 mm as the default value
	At end of treatment, these findings indicate residual disease	When no longer visible, 0 × 0 mm
		For a node > 5 mm × 5 mm, but smaller than normal, use actual measurement for calculation
Nonmeasured lesions	Not applicable	Absent/normal, regressed, but no increase
Organ enlargement	Not applicable	Spleen must have regressed by > 50% in length beyond normal
New lesions	None	None
Bone marrow	Residual uptake higher than uptake in normal marrow but reduced compared with baseline (diffuse uptake compatible with reactive changes from chemotherapy allowed). If there are persistent focal changes in the marrow in the context of a nodal response, consideration should be given to further evaluation with MRI or biopsy or an interval scan	Not applicable
No response or stable disease	No metabolic response	Stable disease
Target nodes/nodal masses, extranodal lesions	Score 4 or 5 with no significant change in FDG uptake from baseline at interim or end of treatment	< 50% decrease from baseline in SPD of up to 6 dominant, measurable nodes and extranodal sites; no criteria for progressive disease are met

Response and Site	PET-CT-Based Response	CT-Based Response
Nonmeasured lesions	Not applicable	No increase consistent with progression
Organ enlargement	Not applicable	No increase consistent with progression
New lesions	None	None
Bone marrow	No change from baseline	Not applicable
Progressive disease	Progressive metabolic disease	Progressive disease requires at least 1 of the following
Individual target nodes/nodal masses	Score 4 or 5 with an increase in intensity of uptake from baseline and/or	PPD progression: An individual node/lesion must be abnormal with: LDi > 1.5 cm and Increase by \geq 50% from PPD nadir and An increase in LDi or SDi from nadir 0.5 cm for lesions \leq 2 cm 1.0 cm for lesions $>$ 2 cm In the setting of splenomegaly, the splenic length must increase by $>$ 50% of the extent of its prior increase beyond baseline (eg, a 15-cm spleen must increase to $>$ 16 cm). If no prior splenomegaly, must increase by at least 2 cm from baseline New or recurrent splenomegaly
Extranodal lesions	New FDG-avid foci consistent with lymphoma at interim or end-of-treatment assessment	New or recurrent splenomegaly
Nonmeasured lesions	None	New or clear progression of preexisting nonmeasured lesions
New lesions	New FDG-avid foci consistent with lymphoma rather than another etiology (eg, infection, inflammation). If uncertain regarding etiology of new lesions, biopsy or interval scan may be considered	Regrowth of previously resolved lesions A new node $>$ 1.5 cm in any axis A new extranodal site $>$ 1.0 cm in any axis; if $<$ 1.0 cm in any axis, its presence must be unequivocal and must be attributable to lymphoma Assessable disease of any size unequivocally attributable to lymphoma
Bone marrow	New or recurrent FDG-avid foci	New or recurrent involvement

- Abbreviations: 5PS, 5-point scale; CT, computed tomography; FDG, fluorodeoxyglucose; IHC, immunohistochemistry; LDi, longest transverse diameter of a lesion; MRI, magnetic resonance imaging; PET, positron emission tomography; PPD, cross product of the LDi and perpendicular diameter; SDi, shortest axis perpendicular to the LDi; SPD, sum of the product of the perpendicular diameters for multiple lesions.
- A score of 3 in many patients indicates a good prognosis with standard treatment, especially if at the time of an interim scan. However, in trials involving PET where escalation is investigated, it may be preferable to consider a score of 3 as inadequate response (to avoid undertreatment). Measured dominant lesions: Up to six of the largest dominant nodes, nodal masses, and extranodal lesions selected to be clearly measurable in two diameters. Nodes should preferably be from disparate regions of the body and should include, where applicable, mediastinal and retroperitoneal areas. Non-nodal lesions include those in solid organs (eg, liver, spleen, kidneys, lungs), GI involvement, cutaneous lesions, or those noted on palpation. Nonmeasured lesions: Any disease not selected as measured, dominant disease and truly assessable disease should be considered not measured. These sites include any nodes, nodal masses, and extranodal sites not selected as dominant or measurable or that do not meet the requirements for measurability but are still considered abnormal, as well as truly assessable disease, which is any site of suspected disease that would be difficult to follow quantitatively with measurement, including pleural effusions, ascites, bone lesions, leptomeningeal disease, abdominal masses, and other lesions that cannot be confirmed and followed by imaging. In Waldeyer's ring or in extranodal sites (eg, GI tract, liver, bone marrow), FDG uptake may be greater than in the mediastinum with complete metabolic response, but should be no higher than surrounding normal physiologic uptake (eg, with marrow activation as a result of chemotherapy or myeloid growth factors).

† PET 5PS: 1, no uptake above background; 2, uptake \leq mediastinum; 3, uptake $>$ mediastinum but \leq liver; 4, uptake moderately $>$ liver; 5, uptake markedly higher than

